5. PLANNED ANALYSES

5.1. Planned Interim Analyses

Interim analyses are based on locked data and performed as appropriate to support commercial approval of bardoxolone methyl. A database lock plan will describe the details of each database lock. All outputs identified in this SAP and planned for the final analysis will be prepared for each interim analysis, and an interim CSR will be prepared.

At the time of each planned interim analysis, no individual patient's data are considered fully locked; therefore, interim results are interpreted as preliminary.

5.2. Final Analyses and Reporting

All final, planned analyses identified in this SAP will be performed after the last patient has completed the study and the database has been locked. A final CSR will be prepared based on the final analyses.

6. GENERAL CONSIDERATIONS FOR DATA ANALYSES AND HANDLING

Results will be summarized by the treatment analysis groups described in Section 4.5.

Patient listings of all analysis data that support summary tables and figures are provided. Measurements from patients excluded from the pre-defined analysis sets are not included in summary tables unless specified otherwise, but they are included in the patient listings. Missing data are not imputed, unless otherwise specified. In general, patient listings are sorted by patient number and assessment date (time and parameter, as applicable).

6.1. General Summary Table and Individual Subject Data Listing Considerations

Results of statistical analyses are reported using summary tables, listings, and figures (TLFs). All TLFs will use ICH numbering conventions.

Results will be pulled from RANGER analysis datasets.

All analyses and summaries are produced using SAS[®] version 9.3 (or higher).

6.2. General Post Text Summary Table and Individual Subject Data Listing Format Considerations

Unless otherwise specified, descriptive statistics for continuous variables include the number of patients with data (N), mean, standard deviation (SD), median, minimum, and maximum. The same number of decimal places as in the observed value are presented when reporting minimum and maximum; 1 more decimal place than in the observed value is generally presented when reporting mean; and 2 more decimal places than in the observed value are presented when reporting SD. When calculating the minimum and maximum of average baseline values, the same number of decimal places as in the observed value will be presented when reporting minimum and maximum. For imputed values and the average of baseline values, the average values will be rounded to the same number of decimal places as the source value.

Categorical (qualitative) data are presented using frequency counts and percentages. All percentages are rounded to 1 decimal place, unless otherwise specified. Percentages equal to 100 are presented as 100% and no percentages are presented for zero frequencies. Where individual variable values are missing, summaries of categorical data are based on reduced denominators (i.e., only patients with available data are included in the denominators). For summaries of AEs and concomitant medications, the percentages are based on the number of patients who received study drug within each summary group.

6.3. Analysis Populations

Analysis populations defined in this section pertain to patients enrolled in the RANGER portion of the trial.

6.3.1. Enrolled Population

The enrolled population will include all enrolled patients, regardless of whether a patient took any dose of bardoxolone methyl. A patient is considered enrolled if informed consent form is obtained. The set of enrolled patients will be used for study population summaries.

6.3.2. Safety Population

The safety population includes all patients who received at least 1 dose of bardoxolone methyl.

6.3.3. Subgroups

The 6-minute walk test, Borg dyspnea index, and WHO/NYHA functional class assessment are summarized separately using the following subgroups:

- Geographic location: US; Other
- Sex: female; male
- Race: (White, Non-White)
- Ethnicity: Non-Hispanic/Latino; Hispanic/Latino
- CTD; non-CTD

Safety summaries are summarized by CTD; non-CTD.

6.4. Baseline Definition

Last measurement on or prior to the date of first study drug administration is considered the RANGER Day 1 measurement for the calculation of baseline. If a baseline value is missing, the last available value in the LARIAT or CATALYST study will be used as baseline.

6.5. Derived and Transformed Data

6.5.1. Connective Tissue Disease (CTD) Etiology

Subgroups include summaries by CTD and non-CTD status. In addition, baseline characteristics summaries include connective tissue disease (CTD) etiology (none, scleroderma, lupus, mixed, and other). Patient's etiology is derived from the baseline characteristics in the prior study in which he or she participated (LARIAT or CATALYST). For patients participating in CATALYST or LARIAT, PH etiology values are the values recorded at the CATALYST or LARIAT Screening visit.

Subject's age in years will be calculated based on date of informed consent date using the following formula:

$$\text{Age (year)} = \text{FLOOR} (\text{date of informed consent} - \text{date of birth}) / 365.25 * 12)$$

where FLOOR () function returns the integer part of the result.

6.5.2. Baseline Age

Subject's age in years is defined as the age at RANGER study consent (RANGER Day 1 for LARIAT patient, RANGER Day 1 for CATALYST patient). If no date of RANGER study consent is present, the age at RANGER Day 1 visit is used.

$$\text{Age (year)} = \text{Floor} ((\text{date of extension study consent} - \text{date of birth})/365.25)$$

6.5.3. Study Day

Study day is the day relative to the date of first study drug kit dispensation in RANGER study, which may precede the date of first dose of study drug. Day 1 is defined as the date of study drug kit dispensation in RANGER study, unless otherwise specified for the calculation of baseline (Section 6.4).

Assessments that occur after RANGER study drug dispensation but before the first study drug administration are considered to occur on study Day 1. Assessments collected on the same date as the first date of study drug administration will be considered to occur before the first dose of study drug administration.

For visits (or events) after the date of drug dispensing, day is calculated as:

- Study day = visit (or event) date - date of drug dispense + 1

For visits (or events) before the date of drug dispensing, day is calculated as:

- Study day = visit (or event) date - date of drug dispense

For listings (such as for adverse events) the quantity 'days since first (or last dose)' is defined as:

- days since first (or last dose) = event date – date of first (or last dose) + 1

For summaries that present distribution of time expressed in weeks and months, weeks will be defined as days divided by seven and months as days divided by 30.4.

6.5.4. Change from Baseline

Change from baseline is calculated using the baseline value (Section 6.4) and the value closest to the target study day, using the rules defined in Section 6.5.5.

Change from baseline is calculated as (post-baseline result – baseline result).

Percent change from baseline is calculated as (change from baseline/baseline result * 100).

If either the baseline or the post-baseline result is missing, the change from baseline and/or percentage change from baseline is set to missing as well.

6.5.5. Visit Windows

Because clinical visits may occur outside protocol-specified windows, instead of relying on visit labels in the clinical database, analysis visits and their windows are defined using derived study day (Section 6.5.3). Study day is calculated using the actual date for each scheduled and unscheduled assessment and compared to the target study day for each analysis visit. Data analysis and summaries are based on the collection date that is closest to the protocol scheduled target study day (Table 3).

Table 3: Analysis Visits

Analysis Visit	Label	Target Study Day	Analysis Window
0	Day 1	1	1
1	Week 1	7	$2 \leq \text{Study Day} \leq 10$
2	Week 2	14	$11 \leq \text{Study Day} \leq 21$
4	Week 4	28	$22 \leq \text{Study Day} \leq 35$
6	Week 6	42	$36 \leq \text{Study Day} \leq 49$
8	Week 8	56	$50 \leq \text{Study Day} \leq 70$
24	Week 24	168	$140 \leq \text{Study Day} \leq 196$
48	Week 48	336	$308 \leq \text{Study Day} \leq 364$
72	Week 72	504	$476 \leq \text{Study Day} \leq 532$
96	Week 96	672	$644 \leq \text{Study Day} \leq 700$
120, 144, etc.	Week 120, Week 144, Every 24 Weeks Thereafter	Analysis Visit x 7	$([\text{Analysis Visit} \times 7] - 28) \leq \text{Study Day} \leq ([\text{Analysis Visit} \times 7] + 28)$
FU	Follow-up	28 days after last dose	$14 \leq \text{Days after last dose} \leq 35$

The safety follow-up is based on days since last dose. If more than one assessment exists during the follow-up after last dose, the one closest to 28 days following the date of the last study drug administration is used for analysis and summary.

If a parameter is assessed or measured more than once within a visit window, the one that is closest to the protocol-scheduled time point (or target study day) is used for the purposes of data analysis and summary. If two assessments are equidistant from a target study day, the earlier assessment is used. If the visit used for analysis includes two assessments on the same day, the average of the two measurements will be used.

Records from visits not closest to the target study day, and therefore not used in analyses, are presented in by-subject data listings.

6.6. Handling of Missing Data

6.6.1. Missing Data

Missing data are not imputed.

6.6.2. Missing Start and Stop Dates for Prior and Concomitant Medication

Missing start dates for concomitant medications are not imputed.

Concomitant medications with incomplete end dates are considered concomitant medications if:

- Day and month are missing, and the year is equal to or after the year of the first date of study drug administration;
- Day is missing and the year is after the year of the first date of study drug administration;
- Day is missing and the year is equal to the year of the first date of study drug administration and the month is equal to or after the month of the first date of study drug administration; or
- Year is missing.

6.6.3. Missing Start and Stop Dates for Adverse Events

Treatment-emergent adverse events (TEAEs) are events that either:

- Had a date of onset on or after the date of the date of first dose of study drug and not more than 30 days after the date of the last dose of study drug, or
- Had no recorded date of onset with a stop date after the first dose of study drug, or
- Had no recorded date of onset or stop date.

Adverse events with incomplete start dates are considered after the date of first dose if:

- Day and month are missing, and the year is equal to or after the year of the first date of study drug administration;
- Day is missing and the year is after the year of the first date of study drug administration;
- Day is missing and the year is equal to the year of the first date of study drug administration and the month is equal to or after the month of the first date of study drug administration; or
- Year is missing.

Adverse events with incomplete start dates are considered on or within 30 days of last dose, if:

- Day and month are missing, and the year is equal to or before the year of the date of last dose of study drug plus 30 days;
- Day is missing and the year is equal to or before the year of the date of last dose of study drug plus 30 days, and month is equal to or before the month of the date of last dose of study drug plus 30 days;
- Year is missing.

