9.1. Adverse Event Preferred Term and Body/Organ System Summary Tables

AEs are summarized by treatment analysis group as defined by the safety analysis set. General considerations for AE summaries and calculations are:

- Multiple events by preferred term (PT) and system organ class (SOC) are counted once only per patient for each treatment analysis group.
- For summaries by severity, only the most severe event is counted per patient for each treatment analysis group.
- For summaries by relationship, for frequency counts by patient, only the most related event is counted per patient for each treatment analysis group.
- An AE with a missing resolution date or incomplete date that is not identified as continuing is assumed to be continuing and no duration is calculated.
- Only treatment-emergent adverse events (TEAEs) are included in summaries.

AEs are coded using MedDRA (Medical Dictionary for Regulatory Activities) version 19.0. In MedDRA, each verbatim term is mapped to a preferred term and high level term (HLT), which is then mapped to a system organ class. Tables and listings present data at the SOC and PT level.

Treatment-emergent adverse events (TEAEs) are events that either:

- Had a date of onset on or after the date of the date of first dose in the RANGER study and not more than 30 days after the date of the last dose of study drug in the RANGER study, or
- Had no recorded date of onset with a stop date after the first dose of study drug, or
- Had no recorded date of onset or stop date.

Adverse events with a date of onset in LARIAT or CATALYST that continued during the RANGER study are not considered TEAEs.

In addition, adverse events which occurred >30 days after the date of last dose of study drug are listed as late-onset AEs (LOAEs). These are adverse events that had a date of onset more than 30 day after the date of the last dose of study drug.

The investigator grades the severity of the AEs as mild, moderate, or severe as defined in the study protocol Section 11.5.

Association or relatedness to the study medication are graded by the investigator according to criteria specified in Section 11.4 of the study protocol.

As defined in the protocol and captured on the CRF, a serious adverse event (SAE) is an adverse event that results in any of the following:

- Death;
- A life-threatening adverse drug experience;
- Inpatient hospitalization or prolongation of existing hospitalization;

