9.1.1. Missing and Partial AE Onset Dates

Rules for handling missing partial AE Onset Dates are included in Section [6.6.3](#).

9.1.2. Summaries of Adverse Events for Serious Adverse Events (SAE), Adverse Event Dropouts, and Death

Treatment-emergent AEs are summarized by treatment analysis group at onset of the AEs. For each treatment analysis group, SOC, and PT, the number and percentage of patients reporting an event are calculated. For subgroups, the number and percentage of patients reporting an event within a subgroup are calculated. In summary tables, SOC are presented alphabetically and events within SOC are presented by decreasing frequency count.

Summary tables (number and percentage of patients) of AEs (by SOC and PT) are provided by treatment analysis group as follows:

- All treatment-emergent AEs
- All treatment-emergent related AEs (definitely, probably, or possibly related)
- All treatment-emergent AEs by severity
- All treatment-emergent serious adverse events (including deaths)
- All related treatment-emergent serious adverse events (including deaths)
- All treatment-emergent adverse events leading to permanent discontinuation of study drug.

Listings are provided showing:

- All AEs
- Serious adverse events (including deaths)
- AEs leading to discontinuation of study drug.

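### The missing-day rule for adverse event onset applies its month test in every year, so on-treatment events from earlier years drop out of all TEAE tables

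*SAP*

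**What the plan says.** SAP 6.6.3 defines a treatment-emergent adverse event (TEAE) mainly as one with onset on or after first dose "and not more than 30 days after the date of the last dose of study drug, or" one that meets either of two fallback criteria for events with no recorded onset. It then gives two sets of rules for incomplete start dates.

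- **Lower bound (after first dose).** Missing-day onsets are covered by two bullets. One is for later years and has no month test: "Day is missing and the year is after the year of the first date of study drug administration". The other compares months only when the year equals the first-dose year.
- **Upper bound (on or within 30 days of last dose).** A single bullet covers missing-day onsets. It opens "Day is missing and the year is equal to or before the year of the date of last dose of study drug plus 30 days". Its second half adds the month condition: "and month is equal to or before the month of the date of last dose of study drug plus 30 days".

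SAP 9.1.1 relies on these rules: "Rules for handling missing partial AE Onset Dates are included in Section" 6.6.3. SAP 9.1 sets the consequence: "Only treatment-emergent adverse events (TEAEs) are included in summaries". SAP 2 makes the SAP govern where it and the protocol differ on planned analyses.

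**The concern.** The upper-bound bullet joins its year test and its month test with a plain AND. An onset in an earlier year therefore passes on year but is still rejected if its calendar month is later than the cutoff month. Whether a true on-treatment event is counted then depends on the time of year it began.

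Two features of the section show a slip rather than a chosen convention. The lower-bound rule separates the two cases correctly. The neighbouring bullets also keep less precise dates: an onset known only as 2018 is retained, while one known as November 2018 is lost, so better information removes the event.

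The frequency, intensity and relatedness of AEs and SAEs make up the first part of the primary safety endpoint (SAP 3.2.1). Affected events would be missing from every table in SAP 9.1.2: all TEAEs, related, by severity, serious, related serious, and leading to discontinuation.

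**Working it through.** The plan gives no figure to reproduce, and because the study is descriptive no power or alpha calculation applies. The check is of date logic.

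**Inputs**
- Rule and TEAE window: SAP 6.6.3.
- Example last dose: 30 March 2020, the termination date and the imputed end date in SAP 6.6.4. Last dose + 30 days = 29 April 2020.
- Example first dose: July 2017, the estimated first enrolment in Germany (Protocol Synopsis). This is an assumption, varied below.

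**Formulas.** Let y, m be the onset year and month, and Y, M those of last dose + 30 days.
- SAP rule: y ≤ Y and m ≤ M.
- Chronological rule: y < Y, or (y = Y and m ≤ M).

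Any date that passes the SAP rule also passes the chronological rule: either y < Y, or y = Y with m ≤ M. The reverse is false. So the SAP rule can only remove events.

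**Single case.** Onset November 2018, with Y = 2020 and M = 4.
- SAP rule: 2018 ≤ 2020 is true, 11 ≤ 4 is false, so the event is excluded.
- Chronological rule: 2018 < 2020, so it is included. Onset was about 16 months before last dose.
- An onset of February 2018 passes both rules.

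**Count for first dose July 2017, last dose 30 March 2020.**
- Eligible months: 6 (2017) + 12 (2018) + 12 (2019) + 4 (2020) = 34.
- Excluded: July–December 2017 (6) + May–December 2018 (8) + May–December 2019 (8) = 22.
- 22/34 = 64.7%.

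**Other dates, counted the same way**

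| First dose | Last dose | Cutoff | Excluded / eligible months | Share |
|---|---|---|---|---|
| Jan 2017 | 30 Mar 2020 | 29 Apr 2020 | 24/40 | 60.0% |
| Jul 2017 | 30 Mar 2020 | 29 Apr 2020 | 22/34 | 64.7% |
| Jan 2018 | 30 Mar 2020 | 29 Apr 2020 | 16/28 | 57.1% |
| Jan 2019 | 30 Mar 2020 | 29 Apr 2020 | 8/16 | 50.0% |
| Jul 2019 | 30 Mar 2020 | 29 Apr 2020 | 6/10 | 60.0% |
| Jan 2020 | 30 Mar 2020 | 29 Apr 2020 | 0/4 | 0% |
| Jul 2017 | 15 Oct 2019 | 14 Nov 2019 | 2/29 | 6.9% |
| Jul 2017 | 15 Nov 2019 | 15 Dec 2019 | 0/30 | 0% |
| Jul 2017 | 15 Dec 2019 | 14 Jan 2020 | 28/31 | 90.3% |

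The loss is greatest when the cutoff falls early in a year and vanishes when it falls in December.

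**Does another clause recover these events?** The fallback criterion "Had no recorded date of onset with a stop date after the first dose of study drug, or" needs an onset that was not recorded. A month and year is a recorded, incomplete onset, so it does not clearly apply. SAP 9.1 and 9.1.1 add no correction.

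**The case against.** - **Another reading.** If the month of last dose plus 30 days means a dated month (April 2020), then November 2018 precedes it and passes. That reading makes the year clause redundant and does not fit the neighbouring bullets, which treat year and month separately. The documents do not show how the rule was programmed, so the finding concerns the text as written.
- **Listings keep the events.** SAP 9.1.2 plans listings of all AEs, SAEs and AEs leading to discontinuation, not restricted to TEAEs. This is true and limits the loss to the summary tables, but those tables carry the reported frequencies.
- **The size in events is unknown.** This stands. Only onsets with month and year known and day missing are affected, and there may be few. Missing days should be uncommon for SAEs, which are reported within 24 hours of site awareness (Protocol 11.7), and less likely during the closely monitored first 8 weeks.
- **Onsets may not be even over time.** Protocol 5.2.2 to 5.2.4 describe some effects clustering soon after treatment starts, mostly in earlier studies in other populations. With an April 2020 cutoff, clustering could act either way: a July 2017 starter loses all of the first six calendar months, while a January 2018 starter keeps the first four.
- **Not every patient has an April cutoff.** SAP 9.2 takes the last kit dispensing date as last dose for patients still on treatment at a data cut, and patients first dosed in 2020 lose nothing with an April 2020 cutoff. This changes who is affected, not the fault.

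**Conclusion.** The concern holds. Read literally, SAP 6.6.3 rejects missing-day onsets from earlier years whenever their calendar month is later than the cutoff month, and nothing else in the SAP restores them. For a last dose on 30 March 2020, onsets in May to December of every earlier year are lost, which is 50% to 65% of eligible calendar months for the first-dose dates examined from January 2017 to July 2019. Over all the dates examined the range is 0% to 90%.

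These shares apply only to AEs with a missing day. They equal shares of events only if onsets are spread evenly over months. The direction needs neither assumption: the rule can only understate TEAE counts. Because it is a deterministic error in the tables for the primary safety endpoint and costs almost nothing to repair, it must be fixed.

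**What to change.** Replace the single upper-bound bullet for missing-day onsets in SAP 6.6.3 with two, matching the first-dose rule:

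- day missing, and onset year earlier than the year of (last dose + 30 days); or
- day missing, onset year the same as the year of (last dose + 30 days), and onset month no later than the month of that date.

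In the July 2017 to 30 March 2020 case this restores all 22 months and adds no false inclusions. The cost is one SAP bullet and one line of code. Make the change before database lock. If the lock has passed, identify it as a post-lock change, as SAP 2 requires, and rerun the TEAE tables. Reporting how many AEs have a missing day, and how many change status, would show the actual effect.

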6.6.4. Missing Treatment or Study End Date

The study was terminated on March 30, 2020. If the treatment end date or study end date are missing, the date will be imputed as March 30, 2020. If the treatment end date or study end date are missing and no reason for treatment or study discontinuation are included in the CRF, the reason for treatment or study discontinuation will be study termination.

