### **8.3. Patient Discontinuation and Termination**

Patients have the right to discontinue study drug or withdraw from the study at any time for any reason, without prejudice to their medical care. Furthermore, the investigator may discontinue a patient from study drug. Consultation with the medical monitor should occur prior to study drug discontinuation or withdrawing a patient from the study. The reason for a patient's discontinuation from study drug or study termination will be recorded in the electronic case report form (eCRF).

Discontinuation refers to a patient's stopping administration of study drug and all study assessments and visits. Reasons for study drug discontinuation may include the following:

- Occurrence of an AE or change in medical status that will lead the investigator to be concerned about the patient's welfare;
- Administrative reasons (*e.g.*, inability to continue);
- Sponsor termination of the study;
- Voluntary withdrawal;
- Females who become pregnant during the study;
- Premature termination or suspension of an investigational site;
- Loss to follow-up;
- Death;
- Withdrawal of consent.

Patients must discontinue study drug if any of the following occur.

- ALT or AST > 8X ULN;
- ALT or AST > 5X ULN for more than 2 weeks;
- ALT or AST > 3X ULN and (total bilirubin > 2X ULN or International Normalized Ratio [INR] > 1.5);
- ALT or AST > 3X ULN with the appearance of fatigue, nausea, vomiting, right upper quadrant pain or tenderness, fever, rash, and/or eosinophilia (> 5%).

Patients who discontinue from the study will be asked to complete the End-of-Study procedures noted in [Table 3](#).

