7.2. Subjects Disposition

A disposition summary includes the number and percentage of patients in the following categories:

- Patients with prior participation in LARIAT
- Patients with prior participation in CATALYST and randomized to placebo (only summarized when unbinding of CATALYST has occurred)
- Patients with prior participation in CATALYST and randomized to bardoxolone methyl (only summarized when unblinding of CATALYST has occurred)
- Continuing (or complete) treatment
- Terminate from the study
 - Reason for terminating study

Results will be summarized by analysis population (Section 6.3). A listing of disposition is provided for all enrolled patients.

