9.2. Exposure and Compliance

The duration of study drug exposure is defined as the number of days on treatment analysis group from the first dose of study drug until the last dose of study drug (last dose - first dose + 1). Study drug exposure is summarized by descriptive statistics. Summaries include the total dose (mg) received (based on the number of pills returned), study drug compliance, the number and percentage of patients receiving study drug by scheduled dispense visit (reference visit window table), and duration (days) of exposure during the study treatment period.

In addition, a summary of the number and percentage of patients on bardoxolone methyl by visit and dose (5 mg, 10 mg) is generated.

Total number of doses dispensed and total dose (mg) dispensed are calculated from total number of kits (bottles) recorded on the Study Drug Dispensation eCRF. Total number of doses received are calculated from information on the eCRF of Study Drug Return and Study Drug Dispensation, as the total number of doses dispensed – total number of doses returned. Study drug compliance (%) is calculated as $100 \times \text{total number of doses received} / \text{total number of doses dispensed}$. For patients who remain on study treatment at the time of an interim or final data cut, the last kit dispensed date is considered the date of last dose.

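### SAP 6.6.4 dates every missing treatment or study end as 30 March 2020, and calls it study termination if no reason is recorded, without checking when the patient was last seen

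*SAP*

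**What the plan says.** SAP 6.6.4 states: "The study was terminated on March 30, 2020". It continues: "If the treatment end date or study end date are missing, the date will be imputed as March 30, 2020". The date rule also stands in the SAP's Technical Summary Report. If, in addition, "no reason for treatment or study discontinuation are included in the CRF", then "the reason for treatment or study discontinuation will be study termination". No further condition is attached.

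The assigned reason is reported. SAP 7.2 lists "Reason for terminating study" as a row of the disposition summary. Protocol 8.3 gives "Loss to follow-up", death, voluntary withdrawal and sponsor termination of the study as separate reasons. It also says that the reason for discontinuation "from study drug or study termination will be recorded in the electronic case report form".

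Exposure is handled elsewhere. SAP 9.2 counts it from first dose to last dose. For patients who remain on study treatment at an interim or final data cut, "the last kit dispensed date is considered the date of last dose". The treatment-emergent adverse event (TEAE) window in SAP 6.6.3 and 9.1 closes 30 days after last dose.

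**The concern.** The rule turns an unknown reason into a known one, and the one it picks is administrative. The study is open-label and descriptive, and long-term tolerability is part of its stated purpose, so readers will use the disposition table to see how many patients left and why. Under 6.6.4, a patient who stopped attending in 2019 and has no end-of-study record cannot be told apart from one who was on treatment when the sponsor closed the study. The SAP asks for no flag or count of imputed cases, so the clinical study report need not show how many there are.

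The date rule reaches further than the reason rule. It applies whether or not a reason was recorded, so a patient with a recorded loss to follow-up or death but a blank date is placed on study until 30 March 2020.

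**Working it through.** The plan gives no figure that depends on this rule, so there is nothing to reproduce. The check is to apply the rule to the kinds of patient it can meet, then to follow the dates for one assumed patient.

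**Cases under SAP 6.6.4**

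- Date and reason both blank, patient attending up to termination: 30 March 2020, study termination. This is right.
- Date and reason both blank, patient last seen well before: 30 March 2020, study termination. The date is wrong and the reason has no support in the data.
- Reason recorded (for example loss to follow-up or death), date blank: the reason is kept and the date becomes 30 March 2020. The date is wrong if the patient left earlier.

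**Dates for one patient (assumed)**

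Inputs: first dose 16 July 2018, an assumption that borrows the date of Protocol version 3; imputed date 30 March 2020 (SAP 6.6.4); kits dispensed at Week 24 and every 24 weeks thereafter (Protocol 9.10.10), with target days 168, 336 and 504 (SAP Table 3).

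30 March 2020 is 623 days after 16 July 2018, which makes it Day 624.

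- Last kit Day 168 (30 December 2018): 624 − 168 = 456 days between last kit and imputed end.
- Last kit Day 336 (16 June 2019): 624 − 336 = 288 days.
- Last kit Day 504 (1 December 2019): 624 − 504 = 120 days. This patient missed nothing, since the next visit was due on Day 672, after termination.

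All three receive the same end date and, if no reason is recorded, the same reason.

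**What separates them**

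One visit interval plus the analysis window of SAP Table 3 is 24 × 7 + 28 = 196 days. Counting back from 30 March 2020 gives 16 September 2019. The 120-day patient falls inside that limit; the 288-day and 456-day patients fall outside it.

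**Exposure**

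SAP 9.2 uses last dose − first dose + 1. If the imputed treatment end date is taken as last dose, all three patients have 624 days. If the last-kit rule governs, they have 168, 336 and 504 days, and 6.6.4 adds nothing. The SAP does not say which applies to a patient with a blank end date.

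**The case against.** The strongest reply is that the rule is narrow and often right. It assigns a reason only where the CRF has none. The protocol requires a reason to be recorded, and a recorded loss to follow-up is not overwritten. SAP version 2.0 is dated 5 June 2020, 67 days after termination, so patients still on treatment when the study closed are a plausible source of blank fields. Nothing in the documents shows that blanks come mainly from patients who drifted away. Adverse events leading to permanent discontinuation have their own table (SAP 9.1.2), and disposition is not part of the primary safety endpoint. All of this stands. It limits the likely size, but it does not make the rule correct for a patient who left earlier.

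Three stronger readings are tempting, and the documents do not support them.

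- A reader might infer that the rule certainly adds false exposure. Exposure runs to last dose, not to treatment end, and the last-kit rule may mean that nothing is added.
- A reader might see a contradiction between 6.6.4 and 9.2. The first fills treatment and study end dates; the second sets last dose for patients still on treatment at a cut. They can coexist. What is missing is a statement of how they fit together.
- A reader might conclude that every consequence flatters the drug. Adverse event percentages use patients who received study drug as denominator (SAP 6.2), and SAP 9.1.2 plans counts and percentages of patients rather than rates per patient-year, so longer exposure would not dilute them. A longer TEAE window could only move events from the late-onset listing into the TEAE tables. Only the disposition label could look more benign.

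It is also fair to say that any contact cut-off is a choice. With visits 24 weeks apart, a last visit more than five months before termination is compatible with full attendance, so the cut-off must not be short.

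**Conclusion.** The point holds for disposition and for end dates. As written, 6.6.4 gives a wrong end date to any patient who left before 30 March 2020 with a blank date. It gives an unsupported administrative reason to any such patient whose CRF also holds no reason. This is a stated rule that misfires, not just missing detail.

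Its size is unknown. The documents do not give the number of blank dates or reasons, and the enrolment figure of 366 in SAP 4.3 is a maximum. The gaps of 120, 288 and 456 days illustrate single patients under an assumed first-dose date and do not estimate a trial total.

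An effect on exposure or on the TEAE window is possible only if the programmer uses the imputed treatment end date as last dose. The SAP neither says so nor rules it out, so that part is an ambiguity to close rather than an error shown. The change is worth making because it is cheap and uses data already collected.

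**What to change.** Revise SAP 6.6.4 as follows.

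- Impute 30 March 2020, and assign study termination where no reason is recorded, only if a visit, contact or dispensing is documented within 196 days before that date and no recorded death or other reason points to an earlier exit.
- Otherwise use the last documented contact date, or the date of death. Where no reason is recorded, report the reason as unknown.
- State that the imputed end date does not replace the date of last dose used in 9.2 or in the TEAE window.
- Report the number of patients imputed under each rule, so that a reader can judge the effect of the 196-day limit.

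The cost is a few lines of SAP text and minor programming. The disposition table may look slightly less favourable. Patients who were attending up to termination keep the result they have now.
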